7.4.5 Allowable Therapies

Usual care will be provided throughout the study to all participants. Participants will be asked to report details of usual care received and this will be recorded in the eCRF during study visits. Usual care includes any intervention that would ordinarily be offered within the trial setting. The only exceptions to this are pulmonary rehabilitation and/or specialist breathlessness clinic attendance as these interventions have potential to impact outcome assessment. Pulmonary rehabilitation

referral will be offered to participants following completion of the trial where it is felt appropriate to do so by the site clinicians.

Usual care includes, but is not limited to, any of the following if considered appropriate by the patient's clinician: outpatient clinic attendance; review and support by the specialist nursing team and/or primary care provider; inhaled, nebulised and/or oral treatments for COPD in accordance with national guidance; and home oxygen therapy. Pharmacological or other non-pharmacological breathlessness treatments (e.g. opioids or hand held fan) will not be restricted if considered appropriate by the patient's clinician but use will be documented during study visits.

8. QUALITATIVE STUDY (FEASIBILITY AND IMPLEMENTATION EVALUATION)

Aligned with the revised MRC Complex Interventions Framework, we will use a theory-based approach to explore how mechanisms and context interact and therefore how change is brought about in relation to the intervention.

8.1 Aims

By exploring differences in the acceptability of trial processes and how the intervention is implemented at each centre, we shall identify:

- 1. Key feasibility issues for the design and delivery of a future trial.
- 2. Factors that would impact NHS implementation at-scale, if the intervention is in future found to be effective.

8.2 Methods

8.2.1 Design and methods

We shall investigate these feasibility and implementation issues using semi-structured interviews with a purposive sample of patients, clinicians and service managers at each of the four centres. The six key uncertainties are:

- 1) Willingness of patients to be randomised (and the reasons why/why not).
- 2) Willingness of clinicians to randomise patients (and the reasons why/why not).
- Acceptability of outcome measures, including environmental outcomes that are not directly-related to an individual's health.

- 4) Acceptability of the FanFIRST intervention (to both patients and clinicians) and reasons for variation in intervention fidelity and delivery, in particular how patients' relationship to SABA (as part of their overall COPD management) affects this.
- 5) Feasibility of delivering the FanFIRST intervention during a standard clinical consultation and the feasibility and acceptability of fan provision/purchase by sites (to inform the definitive trial) and NHS services (to inform scaled implementation).
- 6) Whether willingness or acceptability on any of the above factors differs by ethnic group.

8.2.2 Qualitative study population

Two different groups of participants will be invited to take part in semi-structured interviews of maximum 60 minutes duration as below:

Group 1: Adult COPD patients (n=5) who completed, withdrew, or did not start the main RCT, and, optionally, their nominated carer(s)

Group 2: Clinicians (n=3), and service managers (n=2) who were involved in the main RCT. In total 40 participants will be invited across the two groups, and from across the four study sites.

A sampling grid will be constructed to enable a purposive sample inclusive of profession, gender, and ethnicity, and those who did not start, withdrew, or completed.

8.2.3 Identification and informed consent of patient and carer participants (Group 1)

Study site staff will provide patient participants at Day -28 with a qualitative study-specific participant information sheet and informed consent form for them to take away with them. This will allow participants the opportunity (in time and physical capacity) to consider the study, formulate questions and have these answered. At Day 0, after having completed baseline measures, patient participants will be asked if they would like to participate in an interview (if selected) to explore their experiences and views. Informed consent will be taken from all participants expressing a wish to be considered for an interview. The consent form will include an option for patient participants to nominate a carer, who is a relative or friend, to also participate in the interview. Nominated carers will also be provided with an information sheet, and consented-in if the person they care for is later invited to an interview.

Consent will be taken face-to-face with a researcher. Patient participants selected to take part in an interview will be contacted by a member of the site study team in order to arrange a mutually convenient time to have the interview with the researcher based at the University of Hull. Prior to conducting the interview, the qualitative researcher will verbally reconfirm their consent with them.

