6.2.3 Health Economic Assessment

The following measures will be collected and presented to allow a preliminary assessment of the intervention on costs and patient outcomes:

- Health service utilisation will be recorded including: GP attendance, practice nurse attendance, out-patient appointment attendance (consultant), specialist nurse review (out-patient or home-visit), emergency department attendance, hospital admission, hospice admission.
- We will collect data on the duration of intervention delivery and members of staff involved and their grade. We will also collect information on other costs associated with intervention delivery in order to assess the impact of introducing the intervention into routine NHS practice.
- Measures: Data required to estimate health-related utility and QALYs in a subsequent trial will be collected using the EQ-5D-5L and EQ-VAS.

Quality adjusted life years (QALY) will not be calculated due to the short time horizon of this trial and exploratory nature of data collection.

[figure not shown]
6.2.4 Participant Feedback Surveys:

[figure not shown]
- Invitation experience survey. Reasons why patients agree to participate or decline involvement will be explored using a survey. The survey will be given to patients at the end of the recruitment encounter. Responses will be anonymous and therefore the survey should be completed by participants independently and placed in an envelope which is sealed by the participant prior to being returned to site staff. Sealed envelopes will be collated at the sites and returned in batches to HHTU where they will be opened and data analysed.
- Study experience survey. This will be given to participants during their final visit or posted to
 participants at study completion or withdrawal; if they have consented to this aspect on the
 trial consent form. Experience of the study, including reasons for withdrawal if relevant (trial

or intervention) will be explored. A pre-paid postage envelope will be included, addressed to HHTU, for return of the questionnaires.

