7.1 Stage 1: Participant consent, screening and study enrolment (day -28)

7.1.1 Participant Consent

In order to be screened for the study, participants will need to give informed consent. Only participants identified as eligible after screening (see section 4.3 for details on participant identification) will be enrolled onto the trial.

All participants will be given opportunity (in time and physical capacity) to consider the study and what will be required of them in full and to formulate questions following receipt of the participant information sheet (PIS). Any questions will be addressed and answered fully by a member of the site research team. An actual time period for consideration of participation is not specified, as this will be determined in part by the person's condition and circumstances at the time. However, length of time for consideration will usually exceed 24 hours. In the case that a potential participant wishes to enter the study immediately, the researcher will use their judgement on whether this should be facilitated. All potential participants will be given a Participant Feedback Questionnaire to complete and return.

Participants will also be asked if they consent to be invited to participate in qualitative interviews by the site study team. If consent is obtained and the participant is selected to take part in this element of the study, the participant will be provided with an additional qualitative-specific PIS, and given an opportunity to review the information and ask questions. A time limit will not be applied to this process. Selected participants that wish to participate will be asked to also sign a separate informed consent form for this part of the study.

All consent forms will be stored in accordance with local requirements. The original signed copy is to be filed in the ISF; one copy of the consent form(s) will be given to the participant, and one copy will be entered into the participant's clinical record. In addition, a copy will be uploaded into the electronic study database provided by HHTU for central monitoring purposes.

The PI has overall responsibility for informed consent of participants at their site and must ensure that anyone delegated responsibility to conduct informed consent is duly authorised, trained, and competent to undertake consent according to the protocol and GCP.

This study will be conducted in compliance with the protocol, GCP and the applicable regulatory requirements.

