7.2.1 Baseline Visit (Day 0)

All eligible participants from day -28 will be invited to attend the study site for this visit to undergo the following baseline assessments:

- Spirometry and eligibility confirmation (if not completed during day -28 visit, SFP1)
- Vital sign measurement
- Physical examination (general, cardiac and respiratory examinations)
- Safety/Adverse Event (AE) monitoring
- Breathlessness NRSs
- CAT Score
- EQ5D-5L
- Healthcare Resource Utilisation
- Evaluation of usual care received since the last visit
- SABA use: baseline-data download and sync from inhaler sensors, for those without the app

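### Sections 7.1.1 and 8.2.3 conflict on when interview consent is taken, and neither gives patients who decline the trial a route to interview

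*Protocol*

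**What the plan says.** Section 8.2.1 lists six uncertainties for the interviews. The first is "Willingness of patients to be randomised (and the reasons why/why not". Section 8.2.2 defines the patient group as "Adult COPD patients (n=5) who completed, withdrew, or did not start the main RCT" and puts non-starters in the sampling grid.

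Two sections then describe how patients come to be interviewed.

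- **Section 7.1.1**, at trial consent: "Participants will also be asked if they consent to be invited to participate in qualitative interviews by the site study team". Those later selected receive the interview information sheet, have no time limit, and sign a separate form.
- **Section 8.2.3**: "Study site staff will provide patient participants at Day -28 with a qualitative study-specific participant information sheet and informed consent form". It then says: "At Day 0, after having completed baseline measures, patient participants will be asked if they would like to participate in an interview". Consent is taken from everyone interested, in person, before selection.

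Four other places bear on who can be reached.

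- Section 4.4 lets participants who withdraw or complete signal willingness to be interviewed through the Study Experience Survey.
- Section 6.2.4 describes an Invitation Experience Survey on reasons for agreeing or declining, which section 4.3 offers to all patients approached. On that survey it says: "Responses will be anonymous and therefore the survey should be completed by participants independently".
- Section 8.2.5 books interviews under the SIN, which sections 4 and 7.1.2 issue to consenting participants.
- Section 11.2 explains a low eligibility-to-consent ratio by setting questionnaire data beside interview extracts. Table 5 names both sources for that ratio.

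**The concern.** There are two linked problems. First, the two consent descriptions differ in order. One gives the interview sheet and form after selection. The other gives them to everyone at Day -28 and takes consent at Day 0, before selection. A site cannot do both, and which one it follows decides which non-starters can be interviewed.

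Second, the patients best placed to say why they would not be randomised are those who declined, and no described route leads from declining to an interview. The eligibility-to-consent ratio is a traffic-light criterion in section 12.2. If it comes out amber or red, the interviews are meant to supply the fuller explanation and to inform redesign of study materials and procedures. As written, they would draw on people who had agreed to take part. The sixth uncertainty in 8.2.1, whether willingness differs by ethnic group, is weakened in the same way.

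**Working it through.** **1. Number of interviews.** Section 8.2.2 gives 5 patients, 3 clinicians and 2 managers, with 40 in total over four sites. Read per site: 4 × (5 + 3 + 2) = 40, which reproduces the stated total. Read as overall totals, 5 + 3 + 2 = 10, which does not. So there are 4 × 5 = 20 patient interviews.

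**2. Which groups have a route to interview.** Section 7.1.1 requires trial consent before screening. Section 7.2.1 limits the Day 0 visit: "All eligible participants from day -28 will be invited to attend the study site for this visit". Section 7.2.2 places randomisation after baseline measures.

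| Patient group | Permission under 7.1.1 | Day 0 consent under 8.2.3 | Study Experience Survey (4.4) | Invitation survey (6.2.4) |
|---|---|---|---|---|
| Declines the trial | No, gives no trial consent | No, not invited to Day 0 | No | Reasons only, anonymous |
| Fails screening at Day -28 | Yes | No | Not described | Reasons only, anonymous |
| Drops out between Day -28 and Day 0 | Yes | No | If treated as a withdrawal | Reasons only, anonymous |
| Refuses randomisation after baseline | Yes | Yes | If treated as a withdrawal | Reasons only, anonymous |
| Randomised, then completes or withdraws | Yes | Yes | Yes | Reasons only, anonymous |

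Decliners are the only row with no route to interview. Booking adds a further barrier, because a decliner has no SIN. Under 8.2.3 alone, the second and third rows would also lose their route, so the conflict with 7.1.1 has practical consequences.

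**3. Size of the unreached group.** Let C be the number consenting and r the ratio, read as eligible to consented. Then eligible = C × r, non-consenters = C × (r − 1), and their share of the eligible = (r − 1)/r. Take C = 80 from the planned trial size, and r = 6 and 9 from the edges of the amber band in section 12.2.

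- r = 6: 80 × 6 = 480 eligible; 480 − 80 = 400 non-consenters; 5/6 = 83%.
- r = 9: 80 × 9 = 720 eligible; 720 − 80 = 640 non-consenters; 8/9 = 89%.
- r = 3 (an assumed value inside the green band, not given in the protocol): 80 × 3 = 240 eligible; 240 − 80 = 160 non-consenters; 2/3 = 67%.

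**The case against.** The strongest reply is that the protocol covers more than section 8.2.3 suggests, and much of this stands.

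- A reader of 8.2.3 alone might infer that interview consent is possible only at Day 0. Section 7.1.1 contradicts that: permission is sought at trial consent, and the form is signed after selection with no time limit.
- A reader might also infer that screen failures cannot be interviewed. They consent before screening and receive a SIN, so 7.1.1 reaches them.
- The non-starter stratum in 8.2.2 is therefore not empty. It can hold screen failures, people who drop out before Day 0, and people who refuse randomisation after baseline.
- It would be too strong to say that the first uncertainty cannot be answered for decliners. The Invitation Experience Survey is offered to everyone approached, asks for reasons, and is a named source for the ratio.
- Section 7.1.4 places consent at the Day -28 visit, so some people may attend and decline there. Even then, the only later step that 8.2.3 describes is a Day 0 visit to which they are not invited.
- A purposive sample of 20 is not judged by the share of non-consenters it covers, so the counts describe the size of the omitted group and not a sampling shortfall.

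What the reply does not supply is any interview route for a decliner. An anonymous survey cannot be probed or followed up, and section 11.2 assigns the more detailed explanation to the qualitative data. Screen failures had agreed to take part, and those who refuse after baseline are a narrow subset, so neither stands in well for people who said no at invitation.

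**Conclusion.** The point holds in a limited form. Sections 7.1.1 and 8.2.3 contradict each other on the timing and order of interview information and consent, and must be reconciled. Separately, patients who decline the trial have no described route to interview, although the interviews are meant to explain unwillingness to be randomised. The loss is interview depth from decliners; their stated reasons are still collected by survey.

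In the amber band the omitted group would be roughly 400 to 640 people, or 83% to 89% of those eligible. This assumes about 80 consenters, the ratio read as eligible to consented, and non-consenters treated as decliners. Because screen failures consent first and are replaced, consenters should exceed 80, and at a given ratio the counts rise in proportion. The conclusion on routes does not depend on these figures. This is a cheap improvement to the feasibility evidence; it does not affect the randomised comparison.

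**What to change.** 1. Choose one sequence for interview information and consent, and state it identically in 7.1.1 and 8.2.3.
2. At the invitation contact, offer everyone approached, including those who decline, a slip giving permission to be contacted about an interview. Keep it physically separate from the Invitation Experience Survey so that the survey stays anonymous.
3. Allow remote interview consent for patients, as 8.2.4 already does for staff, and add to 8.2.5 a booking identifier for people without a SIN.
4. Reserve some patient places in the sampling grid for decliners, within the existing total of 40.

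The cost is revised wording, one slip and REC approval of it. No extra interviews are needed. The main drawback is that few decliners may agree to be contacted; if so, the number offered the slip and the number accepting should be reported, so that readers can see how far the interviews represent them.

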8.2.4 Identification and informed consent of health care practitioners (Group 2)

Healthcare practitioners who have been involved with the implementation of the intervention will be identified by the central study team. Those that express an interest in taking part will be provided with a PIS and consent form. All participants will be given opportunity (in time and physical capacity) to consider the study and formulate questions. Potential participants will be given the opportunity to have any questions addressed and answered fully by a member of the research team. An actual time period is not specified but this will usually exceed 24 hours between receipt of the PIS and providing consent. Consent for the healthcare practitioner group will be taken either face-to-face with a researcher at the study site, or online using DocuSign.

*DocuSign is a product of DocuSign Inc., a San Francisco based company. DocuSign enables signatures to be captured on a number of electronic devices. Once signed, everyone receives a copy of the document that they can access at any time. Changes cannot be made to the document once fully executed.

8.2.5 Booking of interviews

After a participant has been identified using the sampling grid (for patient participants) or through their involvement with the study for Group 2 participants, the site team will arrange the qualitative interview using an electronic study specific booking system within a restricted access Microsoft Outlook calendar held at HHTU. Access to the booking system will be restricted to the central study team and authorised research staff at the respective study sites. An interview timeslot will be chosen at a time convenient to the participant and qualitative researcher. Site staff will select a time-slot in the booking system and enter only the unique Subject Identification Number (SIN) ensuring that no patient identifiers are recorded. As no personally identifiable data will be entered into the booking calendar, it will be possible to use a central calendar which will cover all the study sites. In order for the qualitative researcher to be able to contact the participant, site staff will enter the participant identifiers (patient name and telephone number) into the REDCap Cloud eCRF database at the time of the participant agreeing to participate in the qualitative study. If it is not possible to book an interview at the time of the first telephone call, the participant can either arrange the interview at a later date by contacting the University of Hull researcher directly, or agree to be contacted by the UoH researcher directly. Only the SIN is to be held outside of the REDCap eCRF database.

8.2.6 Conduct of interviews

The qualitative researcher based at the University of Hull will make contact at a time agreed with the participant to conduct the interview. Both participant groups will be offered the opportunity to have the interview conducted either on the phone or using a video-conferencing platform e.g., Microsoft Teams, or Zoom. For both participant groups, the qualitative researcher will verbally reconfirm consent with the participant at the start of the interview.

The interviews will follow a group-specific topic guide and last approximately 30-60 minutes. Interviews will be recorded on an encrypted Dictaphone and audio files uploaded to a secure HHTU Box folder. Interviews will be transcribed verbatim by a University of Hull (UoH) approved transcription company e.g., one that has confidentiality agreements in place with UoH. Audiorecorded data will be destroyed once transcription and the allocation of unique identifiers have been assigned.

Interviews will be conducted using an interview guide structured using the Theoretical Framework of Acceptability (TFA)³⁰. This theory, developed following a systematic review and consensus group exercise, breaks down the 'acceptability' of delivering or receiving a healthcare intervention into seven component constructs for investigation as listed below:

| 1 | Affective attitude | How an individual feels about the intervention | |
|---|--------------------|---|--|
| 2 | Burden | The perceived amount of effort that is required to participate in | |
| | | an intervention | |
| 3 | Ethicality | The extent to which an intervention fits with an individual's | |
| | | value system | |
| 4 | Intervention | The extent to which an individual understands an intervention | |
| | coherence | and how it works | |
| 5 | Opportunity costs | The extent to which benefits, profits or values must be given up | |
| | | to engage in an intervention | |
| 6 | Perceived | The extent to which an intervention is perceived as likely to | |
| | effectiveness | achieve its purpose | |
| 7 | Self-efficacy | The extent to which a person is confident that they can perform | |
| | | the behaviour(s) required to participate in an intervention | |

The TFA can be applied prospectively, concurrently, or retrospectively, and therefore has sufficient flexibility for use in a process evaluation.

8.2.7 Participant Withdrawal

Participants have the right to withdraw from the study at any time. The investigator(s) or sponsor may withdraw participants from the study only if indicated by a safety/clinical issue that may prevent them taking part in an interview. Participants that choose to withdraw from the study will be reminded that data collected up to that point will be used in the data analysis but that it will be anonymous and will not identify them in anyway. Participants will have consented to this in the ICF following reading the PIS. If participants continue to express concern about having their data used it may be excluded from data analysis wherever possible unless it is deemed to have a significant negative impact on the scientific value of the study findings. All participant study documentation will be kept for monitoring and inspection purposes until the study documentation archiving period has ended in line with regulatory body guidelines.

